	Cycle 1						Cycle 2		Cycle 3		Cycle 4		Cycle 5		Cycle 6		follow-up																																																																																												
	LAU-7b						LAU-7b		LAU-7b		LAU-7b		LAU-7b		LAU-7b		follow-up																																																																																												
	Placebo						Placebo		Placebo		Placebo		Placebo		Placebo		follow-up																																																																																												
Weeks	1	3	4	7	8	11	12	15	16	19	20	23	27																																																																																																
Visits	X	X	X	X	X	X	X	X	X	X	X	X	X	X	X	X	X																																																																																												
Day	-28 to 0	1	21	49	77	105	161	189																																																																																																					

Study Population
	
Study Inclusion Criteria:
 
 • Signed Informed Consent; • Adult men and women (as per State or Province laws) and 18 years and older; • Diagnosis of cystic fibrosis (positive sweat chloride test) or confirmation (can be historical) of two genetic mutations (one mutation on each of the two alleles of the CFTR gene) causing CF; 																																																																																																												

**Study Population
(cont'd)**

- Screening FEV₁ between 40% and 100% predicted value for age, gender and height, in patients capable of properly performing the test, and baseline FEV₁ within 15% of the screening value, indicative of stable pulmonary function at entry;
 - History of pulmonary exacerbations, defined as at least one (1) pulmonary exacerbation in the year prior to Screening which resulted in documented IV or oral antibiotics;
 - Clinically stable patients, i.e. patients that had no change in their standard antibiotic medication within 5 weeks prior to randomization, of which 2 weeks minimum are prior to Screening;
 - Patients are eligible independently of their history of pulmonary *PsA* infection and their *PsA* status at screening. Medical charts will be reviewed for the *PsA* history in the 12 months prior to screening;

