With pulmonary function as the primary efficacy variable, this study is aimed at the population at risk of losing lung function if left on the current standard of care. Consequently, the lower limit of inclusion for the baseline FEV₁ will be set at 40%, and the upper limit at 100% predicted, depicting that patients have a fairly decent pulmonary function at entry. These are values that do not represent mutually exclusive entry criteria with the other inclusions destined to enrich the study population in patients susceptible to experience a PEx episode during the study (see below). PEx episodes and the ensuing lack of proper resolution of inflammatory defense mechanism are responsible for the lung structure losses and associated non-return to pre-PEx lung function in a sizeable proportion of patients. The entry criteria of the study have therefore been set to enrich the study population with patients more susceptible to develop a PEx episode. Based on the newly discovered regulator effect of LAU-7b on key membrane lipids, such as the stabilization of CFTR, the more mildly affected CF patients may benefit as well from LAU-7b therapy. We plan to enroll patients with at least one pulmonary exacerbation in the previous 12 months that required a documented change of antibiotic, whether oral or IV. It is known that patients who required IV antibiotics to treat a PEx episode in the prior year have about a 30% chance of having an IV-treated exacerbation during a 24-week study⁹². In the case of no IV administered antibiotics for PEx, the odds drop by half⁷¹.

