7.3.3 Randomization Scheme and Stratification

Computer-generated randomization sequences will be programmed into the IWRS. At the time of Randomization during Visit 2, not before, the IWRS will assign a randomization number to each patient.

Randomization will be stratified by

- 1- FEV₁ severity collected at the Screening Period (<70% versus ≥70% predicted);
- 2- Number of PEx (all PEx episodes, whether treated by oral or IV antibiotics): ≤3 versus > 3 PEx episodes in prior year; and
- 3- Co-administration or not of Kalydeco® (ivacaftor), Orkambi® (ivacaftor/lumacaftor), Symdeko® (ivacaftor/tezacaftor) or another commercially available CFTR modulator product.

Once stratified, patients will be randomized in a 1:1 double-blinded fashion to either LAU-7b (active) group or the placebo (control) group. Stratification will enable an even distribution of severity and key baseline characteristics among the two treatment groups.

Detailed instructions for randomization will be provided separately.

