8 SELECTION AND WITHDRAWAL OF PATIENTS

8.1 Screening Inclusion Criteria

Patients may be enrolled in and randomized to the study only if they meet all of the following criteria at screening:

1. Signed Informed Consent;
2. Adult men and women (as per State or Province laws) and 18 years and older;
3. Diagnosis of cystic fibrosis (positive sweat chloride test) or confirmation (can be historical) of two genetic mutations (one mutation on each of the two alleles of the CFTR gene) causing CF;
4. Screening FEV₁ between 40% and 100% predicted value for age, gender and height, in patients capable of properly performing the test, and baseline FEV₁ within 15% of the screening value, indicative of stable pulmonary function at entry;
5. History of pulmonary exacerbation, defined as at least one (1) pulmonary exacerbation in the 12 months prior to Screening which resulted in documented IV or oral antibiotic treatment;
6. Clinically stable patients, i.e. patients that had no change in their standard antibiotic medication within 5 weeks prior to randomization, of which 2 weeks minimum are prior to Screening;
7. Patients are eligible independently of their history of pulmonary *PsA* infection and their *PsA* status at screening. Medical charts will be reviewed for the *PsA* history in the 12 months prior to screening;
8. If taking Kalydeco® (ivacaftor), Orkambi® (ivacaftor/lumacaftor), Symdeko® (ivacaftor/tezacaftor) or another commercially available CFTR modulator product, patients must be taking it for a minimum of 3 months prior to screening if naïve to CFTR modulators and 1 month if switched from another CFTR modulator product, and deemed to tolerate it;
9. All patients, whether prescribed pancreatic enzyme replacement therapy or not, are eligible. However, modifications of the dosing regime during the study should be avoided;
10. No change in CF and allowed systemic chronic therapy for a minimum of 5 weeks prior to randomization, of which 2 weeks minimum are prior to screening. Changes in non-CF therapy may be allowed during this period, on a case-by-case basis, after consultation with Laurent Pharmaceuticals. Allowed concomitant diseases and treatment are listed in specific section;

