9.2 Study Visits and Procedures

9.2.1 Screening and Eligibility Assessments (Visit 1, Day -28 to -1):

Within 28 Days of randomization, interested CF patients will undergo a screening session, Visit 1:

1. Verification of identity and age;
2. Prior to any study specific screening activities, all potential patients will sign the Study Informed Consent Form (ICF). The consent forms will comply with all applicable regulations governing the protection of human subjects. An ICF Form, approved by Laurent Pharmaceuticals and the site's institutional review board (IRB) or ethics committee (EC), must be used. At this point, the site assigns a “subject/patient number” to each patient, in order of screening. This will serve to identify the patient for the entire study participation. This is not the randomization number, which is generated by the IWRS at Visit 2, at time of randomization;
3. Confirmation of the CF diagnosis will be obtained, with proper genetic data if available;
4. Verification of all inclusion and exclusion criteria;
5. Obtain medical history including history of prior pulmonary infections, pulmonary exacerbations and their causative pathogens, all recent and current medications and therapies, non-prescription drug intake, pancreatic enzyme quantities (where applicable) as well as vitamin supplementation (types and quantities). Particular attention will be put on obtaining the history of presence or absence of *PsA* in throat or sputum cultures, the dates of start of oral/IV antibiotics taken to treat PEx episodes, both in the 12 months prior to screening. This will help establishing a background exacerbation *PsA* and PEx pattern;
6. Verification of the medications against list of disallowed medications and associated ban periods;

7. Body weight, height, with BMI calculated;
8. Complete Physical examination;
9. A 12-lead ECG;
10. Vital signs including respiratory rate, oxygen saturation and body temperature;
11. A pulmonary function test comprising at a minimum FEV₁, to be performed under the care of a trained study personnel. Three FEV₁ measurements will be collected and the best of three FEV₁ values (according to American Thoracic Society standards) will be recorded. Central review of the expiratory loops will be performed to ensure accurate baseline FEV₁;

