9.3.1 Protocol Definition of a Pulmonary Exacerbation

The presence of a protocol-defined pulmonary exacerbation is defined by the following, the criteria of Fuch et al. ⁹⁴: "Exacerbation of respiratory symptoms": a patient treated with parenteral antibiotics for any 4 of the following 12 signs or symptoms:

Change in sputum	New or increased hemoptysis	Increased cough
Increased dyspnea	Malaise, fatigue or lethargy	Temperature above 38°C
Anorexia or weight loss	Sinus pain or tenderness	Change in sinus discharge

Change in physical
examination of the chest

Decrease in pulmonary function by
10 percent or more from a previously
recorded value

Radiographic changes indicative of
pulmonary infection

This definition is not a guide to determine the need for a given type of treatment (for example: Oral versus IV antibiotics, corticosteroids or no). Each Investigator will determine to the best of its clinical judgement and for the benefit to the patient, the best treatment for the exacerbation episode. However, if indeed an IV antibiotic course is selected based on the severity of the PEx and other factors and the patient can attend the study site prior to starting the IV antibiotics, this will trigger the performance of PEx-specific assessments prior to initiating the IV antibiotic course and at the end of the course. This is outlined below:

9.3.2 Specific additional testing for patients undergoing a pulmonary exacerbation treated with an IV antibiotic treatment cycle.

Prior to starting and after completing the IV antibiotic treatment:

1. Blood sampling for selective biomarkers such as:
 - a. Plasma lipidomics: AA, DHA, calculated AA/DHA ratio and EPA;
 - b. Markers of inflammation in:
 - Whole blood: total white cell count and absolute neutrophil count;
 - Serum: high sensitivity C-Reactive Protein (hsCRP) and serum amyloid A (SAA);
 - Plasma: interleukins IL-1ra, IL-6, IL-8, IL-10, Granulocyte-Colony Stimulating Factor (G-CSF), calprotectin, ceruloplasmin, haptoglobin, and neutrophil elastase antiprotease complexes (NEAPC).
2. Clinical parameters such as FEV₁ percent predicted, weight, with BMI calculated.

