3.15 Analysis of the Secondary Endpoints

For all secondary efficacy endpoints, all the analysis will be based on data obtained at Week 24 or cumulated up to Week 24

Pre-defined Clinical Parameters:

- Count data variables: the number of antibiotic treatments, the number of days of antibiotic treatment (other than chronic inhaled antibiotics already started prior to trial or oral chronic azithromycin, in summary, any antibiotic change required to address worsening of CF symptoms) and the number of PEx and protocol-defined PEx will be tabulated by treatment group and compared using an appropriate count data model, e.g., Mixed ANOVA model (if assumptions of normality and homogeneity of variance appear acceptable), Poisson regression, negative binomial regression, zero-inflated regression, etc., depending on their distribution. The analysis of the number of protocol-defined PEx will also consider the type of antibiotic

prescribed (I.V. vs. oral) and the time spent on study as well as other covariates described below for the time to event data.

- Time to event data variables: the time to first antibiotic use, the time to first PEx and protocol-defined PEx, the time interval between IV antibiotic-treated PEx episodes will be tabulated by treatment group and compared using a Cox proportional hazards model. The model will include treatment group as main effect with covariates for FEV₁ percent predicted category (<70% versus ≥70% predicted), PEx number category in prior year (≤3 versus > 3 PEx episodes), and co-administration or not of Kalydeco® (ivacaftor), Orkambi® (ivacaftor/lumacaftor), Symdeko® (ivacaftor/tezacaftor) or another commercially available CFTR modulator product (all as per entry stratification). A patient without exacerbation before withdrawal or completion of the study is considered censored at the time of withdrawal or completion of the study. If the proportional hazards assumption is violated, a stratified analysis will be conducted using stratified Cox regression. Additionally, Kaplan-Meier methods will be used to produce graphical presentations of the survival (exacerbation-free survival) by treatment group and to estimate cumulative exacerbation-free survival rates by treatment group.
- Relative change (in %) in FEV₁ percent predicted from Baseline to Week 24: analysis of this variable will be similar to that of the primary analysis of the primary efficacy endpoint, i.e. repeated measures mixed model.

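### If patients with only oral-treated exacerbations are eligible, the protocol-defined PEx models should adjust for prior-year IV-treated exacerbation

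*Protocol*

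**What the plan says.** **Eligibility.** The Protocol synopsis asks for "at least one (1) pulmonary exacerbation in the year prior to Screening which resulted in documented IV or oral antibiotics". Protocol 8.1 criterion 5 asks for an episode "which resulted in documented IV or oral antibiotic treatment", and the rationale in Protocol section 6 also accepts either route. Protocol 7.2.1, SAP 2.4 and SAP 2.7.1 criterion 5 instead require an IV-treated episode.

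**Endpoint.** Protocol 9.3.1 defines a protocol-defined PEx as "a patient treated with parenteral antibiotics for any 4 of the following 12 signs or symptoms".

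**Known predictor.** Protocol section 6 says that patients given IV antibiotics for a PEx in the prior year "have about a 30% chance of having an IV-treated exacerbation during a 24-week study". It continues: "In the case of no IV administered antibiotics for PEx, the odds drop by half".

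**Exacerbation history in the design and models.** The stratification factor in Protocol 7.3.3 is "Number of PEx (all PEx episodes, whether treated by oral or IV antibiotics"), split at 3. The Cox model in SAP 3.15 carries it as "PEx number category in prior year (≤3 versus > 3 PEx episodes"), beside FEV₁ class and CFTR modulator use. The Cox model in Protocol 12.4.2 has age category in place of modulator use and also lacks a prior-IV term. The SAP's analysis of the number of protocol-defined PEx takes its covariates from the Cox list. The antibiotic type it also mentions is, on its natural reading, the route prescribed for on-study episodes.

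**Data.** Protocol 9.2.1 has sites record "the dates of start of oral/IV antibiotics taken to treat PEx episodes" over the 12 months before screening.

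**The concern.** The endpoint depends on the route of treatment, and the protocol gives a figure for one route-specific predictor of it. The models use a history term that ignores route. A patient whose only prior-year episode was treated orally and a patient whose only episode was treated by IV fall in the same class, although section 6 gives them clearly different risks. The factor is in neither the strata nor the covariates.

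Time to first protocol-defined PEx and its incidence are secondary endpoints with few expected events. SAP 3.2 tests them at a nominal 5% as signals to be confirmed in Phase 3, so the size of the estimate matters as well as its p-value. If the arms differ by chance in IV history, part of that difference enters the HR. Without prespecification it could be handled only after the fact.

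**Working it through.** The documents give no sample size, event count or power for any exacerbation endpoint, so there is no planned figure to reproduce. The check starts from the risks in section 6.

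**1. Risk without prior IV treatment.** Odds at 30%: 0.30/0.70 = 0.429. Halved: 0.214. Risk: 0.214/1.214 = 17.6%. If a halved probability was meant, the risk is 15%.

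**2. Implied HR, prior IV against none.** Cumulative hazard is −ln(1 − risk). At 30% it is 0.357; at 17.6% it is 0.194; at 15% it is 0.163. The HRs are 0.357/0.194 = 1.84 and 0.357/0.163 = 2.19.

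**3. Expected events.** The share with IV history is not given, so 25% to 75% is assumed. With 136 patients and no treatment effect, a 50% share gives 136 × (0.300 + 0.176)/2 = 32.4. Over the assumed shares and both readings of step 1 the range is 25.5 to 36.6. With a treatment HR of 0.5 (assumed) and a 50% share, the active-arm risks become 1 − √0.70 = 16.3% and 1 − √0.824 = 9.3%. Total events are then 68 × 0.238 + 68 × 0.128 = 24.9. A working range of 20 to 35 is reasonable once dropout is allowed for.

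**4. Chance imbalance.** With 68 per arm and a 50% share, the SD of the between-arm difference is √(2 × 0.5 × 0.5/68) = 8.6 points. The probability of a difference of 10 points or more is about 24%.

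**5. Effect of an imbalance on the HR.** The shift in log HR is approximately the difference in share times ln(HR from step 2).

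| Difference in IV share | HR 1.84 | HR 2.19 |
|---|---|---|
| 10 points | 0.10 × 0.608 = 0.061, factor 1.06 | 0.10 × 0.786 = 0.079, factor 1.08 |

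A 1 SD difference under the first reading shifts log HR by 0.086 × 0.608 = 0.052.

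**6. Against sampling error.** The SE of log HR is about 2/√events: 0.45 at 20 events and 0.34 at 35. So 0.052 is about 12% to 15% of one SE, or roughly 1% to 2% of the variance.

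**7. Simulated Cox model, with and without a prior-IV term** (136 patients 1:1, 3,000 runs per setting, IV share 25% to 75%, both readings of step 1, no dropout, no other covariates):
- Power rises by 0.1 to 1.1 points. At a 50% share and 17.6% risk it goes from 35.8% to 36.5% at HR 0.5, and from 23.2% to 23.5% at HR 0.6.
- The average estimated HR moves by about 1% or less.
- Type I error is 4% to 5% either way.

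With the three strata in the model and 10% dropout, the gain was 0.4 to 0.9 points at HR 0.5 and 1.2 to 1.3 points at HR 0.4. A further run with 10% dropout and IV shares of 30% to 70% showed what adjustment does achieve. The slope of log HR on imbalance falls from about 0.6–0.75 to about 0–0.1. The SD of log HR does not shrink. The result changes side of p = 0.05 in about 4% of trials at HR 0.5 and in 1% to 1.5% under the null.

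**The case against.** The strongest reply is that nothing in the plan is invalid. SAP 3.15 adjusts for all three randomisation factors, and leaving out one more prognostic covariate is ordinary practice. A reader might infer that the omission biases the exacerbation results. The documents do not support that: randomisation makes the expected imbalance zero, and type I error is sound without the term. A typical imbalance is also small beside the sampling error (step 6), and the confidence interval already largely reflects it. This part of the reply stands.

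The eligibility point also stands. Under Protocol 7.2.1, SAP 2.4 and SAP 2.7.1, every patient would have an IV-treated prior episode and a yes/no term would be constant. The improvement applies only if the synopsis, section 6 and 8.1 govern.

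The HR of 1.84 needs care:
- Section 6 takes its two figures from two different cited sources, and odds may mean probability.
- The group without IV treatment is not stated to be patients with an oral-treated episode.
- The outcome is an IV-treated PEx, whereas the protocol-defined event also needs 4 of 12 signs or symptoms.
- No contrast adjusted for FEV₁ or episode count is given, so the existing count category may already capture part of the effect.

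The reply does not show that the covariate is unhelpful. It is a baseline variable, already collected, that the protocol itself names as predictive of the endpoint's defining component. Adjusting for it removes nearly all the dependence of the estimate on its chance imbalance.

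**Conclusion.** The point holds as a cheap improvement, conditional on oral-only patients being eligible. The models for protocol-defined PEx omit the one predictor that the protocol quantifies, and the pooled count cut at 3 cannot separate one oral-treated episode from one IV-treated episode. The loss is in protection against chance imbalance: about 6% to 8% on the HR for a 10-point difference between arms, which has a probability of about 24% at a 50% IV share.

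Two stronger inferences should be resisted. Adding the term would not rescue power for these endpoints: the gain is about 1 point, and simulated power stays well below 80%. The omission also does not touch the trial's success criterion, which SAP 3.14 rests on FEV₁ in the ITT population.

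The sizes rest on assumed IV shares and treatment HRs, and on section 6's figures carrying over to protocol-defined PEx. They do not extend to the all-PEx or antibiotic-use endpoints.

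**What to change.** 1. Reconcile the eligibility text: the synopsis, Protocol section 6 and 8.1 criterion 5 against Protocol 7.2.1, SAP 2.4 and SAP 2.7.1 criterion 5.
2. If patients with oral-treated episodes only are eligible, add prior-year IV-treated PEx (yes/no) as a baseline covariate in the SAP 3.15 Cox and count models for protocol-defined PEx only, beside the stratification factors.
3. Report the balance of this variable by arm in the baseline table.

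If eligibility is settled as IV-only, the yes/no term is constant and step 2 falls away. The number of prior-year IV-treated episodes could be considered instead, but the documents give no figure to support it.

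The cost is one sentence in the SAP and one table row, with no new data. The downside is one more parameter: the Cox model goes from four to five, which at 20 to 35 events leaves 20/5 = 4 to 35/5 = 7 events per parameter.

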2 SCHEDULE OF EVENTS

	Screening	Baseline	Telephone contacts	End-Of-Cycle 1	End-Of-Cycle 2 ¹	End-Of-Cycle 3	End-Of-Cycle 4 ¹	End-Of-Cycle 6	Follow-up (End-Of-Study visit)	Start of PEx Visit ²	End of PEx Visit ²
Day number	Days -28 to -1	Day 1	Days 10, 38, 66, 94, 122, 150	Day 21	Day 49	Day 77	Day 105	Day 161	Day 189 (or early termination)	1st day of IV Antibiotic	Last day of IV Antibiotic
Visit number	Visit 1	Visit 2	N/A	Visit 3	Visit 4	Visit 5	Visit 6	Visit 7	Visit 8	N/A	N/A
Verification of ID and age	X										
Informed consent	X										
Confirmation of CF diagnosis	X										
Inclusion/Exclusion criteria	X	X									
Medical History including detailed PEx history and precise dates	X	X									
Concomitant Meds and verification of disallowed medications	X	X	X	X	X	X	X	X			
Weight, Height (screening only) and Body Mass Index	X	X		X		X		X	X	X	X
Complete Physical Examination	X								X		
Focused Physical Examination		X		X		X		X			
Ophthalmological examination ³	X					X			X		
Night Vision Questionnaire	X			X		X		X	X		
Pulmonary Function Testing (at min. FEV1)	X	X		X	X	X	X	X	X	X	X
12-Lead ECG	X			X		X		X	X		
Vital Signs including respiratory rate, oxygen saturation and temperature	X	X		X		X		X	X		
Hematology ⁴	X	X		X	X	X	X	X	X		
Chemistry ⁵	X	X		X	X	X	X	X	X		
Pregnancy Test for women	X (serum)	X (urine)		X (urine)	X (urine)	X (urine)	X (urine)	X (urine)	X (urine)		
Urinalysis ⁶	X	X		X	X	X	X	X	X		
Sputum ⁷	X					X		X			
Cystic Fibrosis Questionnaire-Revised (CFQ-R)		X				X		X	X		
Matouk Disease Score (at selected sites)		X				X		X	X		

	Screening	Baseline	Telephone contacts	End-Of-Cycle 1	End-Of-Cycle 2 ¹	End-Of-Cycle 3	End-Of-Cycle 4 ¹	End-Of-Cycle 6	Follow-up (End-Of-Study visit)	Start of PEx Visit ²	End of PEx Visit ²
Day number	Days -28 to -1	Day 1	Days 10, 38, 66, 94, 122, 150	Day 21	Day 49	Day 77	Day 105	Day 161	Day 189 (or early termination)	1st day of IV Antibiotic	Last day of IV Antibiotic
Visit number	Visit 1	Visit 2	N/A	Visit 3	Visit 4	Visit 5	Visit 6	Visit 7	Visit 8	N/A	N/A
Lipidomics (AA, DHA, EPA)		X		X				X	X		
Inflammation and oxidative stress markers, ceramides and metabolipidomic markers		X		X				X			
Systemic bone formation/resorption biomarkers (all patients)		X						X			
Lumbar spine bone density (first 24 patients at selected sites)		X							X		
Randomization		X									
Supervised dosing		X									
Dispensing of study drug packs and drug compliance check where applicable		X		X		X					
Reporting of PEx by patients		X	X	X	X	X	X	X	X	X	X
PEx-related biomarkers in Plasma ⁸										X	X
Plasma retinol and RBP ⁹	X	X		X		X		X	X		
Plasma sample for fenretinide C _{min}				X ¹⁰				X ¹⁰			
Adverse Events		X	X	X	X	X	X	X	X	X	X

¹ The Days 49 and 105 visits are simplified visits focused on safety

² Only for patients experiencing episodes of PEx with need for IV antibiotic (as decided by the treating physician)

³ Complete ophthalmological examination: visual acuity, examination for amblyopia, examination of eyelids, conjunctiva, cornea, pupillary reactions to light and accommodation, specific dark adaptation tests, low contrast visual function, lens, vitreous humor, fundus examination of retina and retinal vessels, fundus visualization of optic nerve and macula. If clinically indicated by the ophthalmologist, an electroretinogram will also be performed

⁴ Hematology: CBC, hemoglobin, hematocrit, differentials (absolute and %) and platelets

⁵ Chemistry: creatinine, BUN, total bilirubin, alkaline phosphatase, AST, ALT, GGT, total protein, Na, K, Ca, bicarbonate, phosphate, albumin, glucose, total cholesterol, LDL cholesterol, HDL cholesterol and triglycerides

⁶ Urinalysis: Includes appearance, pH, specific gravity, protein, hemoglobin, urobilinogen, ketones, bilirubin, nitrites, leucocyte esterase and leukocytes

⁷ Sputum: Sputum will be induced with hypertonic saline according to a standardized procedure across sites. Samples will serve for the assessment of presence and/or density of PsA by CFU determination

⁸ Blood sampling for select biomarkers in plasma (such as AA, DHA, EPA, interleukin-1 receptor antagonist (IL-1ra), IL-6, IL-8, IL-10, G-CSF, calprotectin, absolute neutrophils count, ceruloplasmin, haptoglobin, NEAPC, SAA, and hsCRP).

⁹ Plasma retinol and Retinol Binding Protein will be measured for exploratory correlation with the ophthalmological assessments

¹⁰ Blood sampling for C_{min}: Blood samples will be obtained from all patients pre-dose on Days 21 and 161; Blood will be drawn using BD Vacutainer™ spray coated K2 EDTA tubes. Plasma will be harvested and assayed for fenretinide, its active metabolite (4-MPR) and 4-oxo-fenretinide by a validated LC/MS/MS method.

TABLE OF CONTENT

1	SYNOPSIS.....	4
2	SCHEDULE OF EVENTS	10
3	GLOSSARY OF TERMS AND ABBREVIATIONS	16
4	STUDY PERSONNEL	18
5	INTRODUCTION.....	19
5.1	Investigational product.....	19
5.1.1	Rationale for LAU-7b, a novel and improved oral formulation of fenretinide.....	19
